- Demonstrate preliminary skin efficacy as demonstrated by clinical photo evaluation, patient reported outcomes with Dermatology Life Quality Index (DLQI) and skin histopathology with both Grover's disease and psoriasis vulgaris.
- Obtain user comfort and experience with phototherapy system using psychometric survey.

Objective 2 endpoint

- Elucidate keratinocyte and skin T-cell expression, and viability with blue light phototherapy
- Elucidate changes in circulatory T-cells based on flow cytometry and serum cytokines with blue light therapy.

STUDY INTERVENTION(S) / INVESTIGATIONAL AGENT(S):

The DUSA BLU-U (Model 4170) is a Blue Light Photodynamic Therapy Illuminator is intended to provide phototherapeutic light to the body. Blue light therapy is indicated for dermatological conditions such as actinic keratosis (AK) or inflammatory acne vulgaris. The BLU-U is approved by the FDA (K031805) as a Class II medical device. The BLU-U Illuminator to be used in this study is owned by the Northwestern Memorial Hospital Department of Dermatology and stored at the Dermatology Clinic in Chicago.

PROCEDURES INVOLVED:

Patients with Grover's Disease or Psoriasis vulgaris will be enrolled on the study.

In the informed consent process a Dermatologist will discuss Standard of Care treatment options for Grover's Disease or psoriasis vulgaris. If the patient wishes not to participate in this study the SOC treatment will be available to them. If the patient chooses to participate in this study, they may elect to do SOC treatment at any time (ending participation early) or after the phototherapy study visits are complete. Patients receiving SOC phototherapy (other light type, with activator creams, etc) may participate in this study by blocking a small site from their SOC phototherapy which will be treated with the Blue Light therapy in this trial. The Department of Dermatology has standard of care procedures for blocking specific sites during SOC phototherapy. These procedures will be followed if a patient that is enrolled on the study is simultaneously receiving SOC phototherapy for their condition. The clinical research team will consult with the phototherapy team for any patient that is receiving phototherapy.

No procedures in this study are standard of care for Grover's Disease or psoriasis vulgaris. If the symptoms of resolve before all phototherapy sessions are completed, the patient will have their final assessment and will have completed the study.

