After informed consent a patient will be scheduled to start the study sessions immediately (if not on medications) or after a period of two weeks without using medications related to their skin condition. A site on the body will be identified for treatment with Blue Light, this will be the same site treated throughout the study.

The study visits will take approximately 30 minutes and will be done three times a week (at least 23 hours apart) over five weeks (15 visits total). Each session will consist of 16

STU#: STU00210472

minutes of Blue Light phototherapy with the BLU-U device over the affected area. Before starting the first, seventh and after the last session the patient will have a single, 6mm, punch biopsy of a characteristic lesion on the treated side only and a blood draw not exceeding 30 cc or two tablespoons in a visit. Tissue and blood, samples will be collected under the Dermatology Tissue Acquisition and Biorepository (IRB# STU00009443) protocol upon completion of the consent form for STU00009443.

During the first and last study visit the patient will be asked to complete surveys relating to their comfort and experience with the phototherapy symptoms and psychometric surveys of skin-related symptoms and skin-related quality of life.

In addition photographs will be taken of the afflicted areas before the first treatment, on the first visit, third visit after every 3 treatments until the end of the study as outlined in the table below.

Procedure Table

	Blue Light Phototherapy	Biopsy of lesional treated area	Blood Draw	Psychometric and Skin QoL survey	Photographs of afflicted skin area
Visit 0 - Consent					X
Visit 1 - Baseline	X	X	X	X	X
Visit 2	X				
Visit 3	X				X
Visit 4	X				
Visit 5	X				
Visit 6	X				X
Visit 7	X	X	X		
Visit 8	X				
Visit 9	X				X
Visit 10	X				
Visit 11	X				
Visit 12	X				X
Visit 13	X				
Visit 14	X				
Visit 15	X	X	X	X	X
Early completion (If condition resolved before final visit)	X	X	X	X	X

In this single arm, prospective clinical trial patients with Grover’s disease (n=10) will be invited to participate. A baseline biopsy of a characteristic lesion will be performed. Patients will be asked to complete a baseline psychometric survey of skin-related

STU#: STU00210472

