In a parallel single arm, prospective clinical trial patients with psoriasis vulgaris (n=10) will be invited to participate. A baseline biopsy of a characteristic lesion will be performed. Patients will be asked to complete a baseline psychometric survey of skin-related symptoms and skin-related quality of life. A baseline PASI-75 (a well-accepted clinical endpoint for psoriasis severity) will be conducted and across every treatment visit. Patients will then be asked to present to the phototherapy unit at Northwestern Dermatology for 15 total sessions of blue light therapy divided into 3 weekly sessions. The target irradiance is 14 mW/cm² with a total dose of 9 J/cm² requiring ~16 min per treatment. At each treatment session, clinical photos will be taken along with blue-light dosimeter readings at various locations of the body. At the mid-point of the study (7 sessions), an additional biopsy will be taken of a characteristic lesion. At the end-point of the study (15 sessions), a final biopsy will be taken of a characteristic lesion. Patients will be asked to complete psychometric surveys relating to their comfort and experience with the phototherapy symptoms. In addition, they will complete psychometric surveys of skin-related symptoms and skin-related quality of life to compare against baseline. A final PASI-75 will be scored. Subjects on the therapy will be asked to refrain from using any systemic treatments throughout the trial with a 2-week washout period before the start of the trial. Topical treatments may be used, except in the area that is identified for treatment with Blue Light phototherapy provided by this study.

In partnership with Northwestern University's Skin Biology Disease Research Center (one of only 6 in the country), all skin biopsy results will be processed for standard histology as well as immunohistochemistry. All biopsies will be stained for T-cell biomarkers including CD4, CD3, CD5, CD7, CD8 with cell populations counted for biopsies taken at baseline, at the midpoint and at completion of 15 sessions of blue light therapy. Keratinocyte apoptotic biomarkers will also be collected. Serological markers will be drawn both at baseline and after treatment from blue light in both the Grover's disease and psoriasis cohorts for immune-cell related cytokines (TNF- α , C-reactive protein, IL-6, E-selectin, and ICAM-1)

STU#: STU00210472

Procedures performed to lessen the probability or magnitude of risks:

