Blue Light phototherapy sessions will be done in a private clinic room to maintain privacy of the patient. The researchers and patient will wear protective eyewear during use of the BLU-U device. Eyewear will block light with wavelengths of at least 500nm and shorter with an Optical Density (OD) of two or greater as recommended by the DUSA, the manufacturer of the BLU-U.

Photographs taken for the study will not include the full face and will exclude identifying marks such as tattoos. The intent of photographs is to document the efficacy of the treatment and any improvement of the disease.

Standard, sterile technique will be followed for both blood draws and punch biopsies.

Pictures of the psoriatic lesions and Grover's disease will be recorded and stored on research only devices (tablets/iPads). Those images will only be stored and accessed by research personal devices. The photographs will be used to assess whether the blue light therapy has improved the skins disease is psoriasis and Grover's disease.

DATA AND SPECIMEN BANKING

The biopsies and blood draws will not be stored for future use, and will be immediately used to histopathological examination and serological markers. Specimens will only be handled by the research team and the laboratory conducting pathological and histological testing. All research specimens will be labeled with a unique patient identifier, collection date and time.

Upon completion of consent, the biospy samples will also be shared with Dermatology Tissue Acquisition and Biorepository (IRB# STU00009443).

SHARING RESULTS WITH PARTICIPANTS

The results of the biopsies, and serological markers of the immune system will not be shared with the patient. At the end of the study a dermatologist will give an assessment of the patients condition and follow up care instructions if necessary.

STUDY TIMELINES

An individual will participate in the study for approximately 5 weeks. It will take approximately 1 year to enroll all study participates. The data to complete primary analyses is January 2021.

All recruiting will occur at either Northwestern Memorial Hospital (Arkes Pavilion in the outpatient dermatology offices).

INCLUSION AND EXCLUSION CRITERIA

Inclusion Criteria

1. Patient's aged 18-89 at time of enrollment
2. Previous diagnosis of psoriasis vulgaris or Grover's disease

STU#: STU00210472

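### Read as written, immediate use of blood puts a patient's baseline and final serum in different assay runs, so run-to-run variation may enter the Objective 2 before-after change.

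*Combined protocol and SAP*

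**What the plan says.** Data and Specimen Banking sets out sample handling in one sentence: "The biopsies and blood draws will not be stored for future use, and will be immediately used to histopathological examination and serological markers". It has two parts. The first rules out storage for future use; the second says when the samples are used.

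Procedures Involved sets the sampling times: "Before starting the first, seventh and after the last session the patient will have a single, 6mm, punch biopsy", with a blood draw at the same visits. There are 15 visits, three a week for five weeks. On the laboratory work, the same section says "Serological markers will be drawn both at baseline and after treatment from blue light in both the Grover's disease and psoriasis cohorts" and lists TNF-α, C-reactive protein, IL-6, E-selectin and ICAM-1. For the biopsies it plans "cell populations counted for biopsies taken at baseline, at the midpoint and at completion of 15 sessions of blue light therapy".

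The Objective 2 endpoint is a change over time: "Elucidate changes in circulatory T-cells based on flow cytometry and serum cytokines with blue light therapy". Objective 2 also plans to correlate serum markers with histological or clinical improvement.

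Other text points to retained material. Procedures Involved has tissue and blood collected under the Dermatology Tissue Acquisition and Biorepository protocol. The inclusion criteria require willingness to consent to that protocol. Data and Specimen Banking adds: "Upon completion of consent, the biospy samples will also be shared with Dermatology Tissue Acquisition and Biorepository".

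No section describes assay runs, batching, bridging or control samples, duplicates, adjustment for run, or masking of laboratory readers to visit. Specimens are labelled with the collection date and time.

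**The concern.** Objective 2 rests on each patient's own change from baseline. If every blood sample is assayed when drawn, visit and assay run coincide within each patient. A difference in calibration or reagent lot between two runs then looks the same as an effect of blue light. A concurrent control arm assayed in the same runs would help to separate the two, but this design has none.

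What is at stake depends on how run differences behave across patients. If they are independent, they widen the interval for the mean change and weaken the planned correlations. If they tend in one direction, they produce an apparent change where there is none. With 10 patients per cohort there is little averaging to absorb either.

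**Working it through.** The protocol gives no assay SD, coefficient of variation (CV), effect size, alpha or power, so there is no figure of the plan's own to reproduce. The check has two steps: whether separate runs follow from the text, and how much they could matter.

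**1. Timing.** The visit count and frequency come from Procedures Involved; the Monday/Wednesday/Friday pattern is assumed. Visit 1 is day 0, visit 7 is day 14 and visit 15 is day 32. Baseline to final is 32/7 = 4.6 weeks. Serum used at once on day 0 cannot share a run with serum drawn on day 32. For biopsies the step is weaker: tissue can be processed promptly and its sections stained together later.

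**2. Added variance.** Assume a log scale, with s_w the within-run plus biological SD of one measurement and s_run the between-run SD.

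- Same run: Var(change) = 2·s_w²
- Different runs: Var(change) = 2·s_w² + 2·s_run²
- Ratio = 1 + (s_run/s_w)²
- 95% half-width for the mean change, n = 10: 2.262 × SD(change)/√10

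| s_w | Half-width, same run | s_run 0.05 | s_run 0.10 | s_run 0.20 |
|---|---|---|---|---|
| 0.20 | 0.20 | ratio 1.06, 0.21 | ratio 1.25, 0.23 | ratio 2.00, 0.29 |
| 0.30 | 0.30 | ratio 1.03, 0.31 | ratio 1.11, 0.32 | ratio 1.44, 0.36 |
| 0.50 | 0.51 | ratio 1.01, 0.51 | ratio 1.04, 0.52 | ratio 1.16, 0.54 |

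Example: s_w 0.20 and s_run 0.20 give SD(change) = √(0.08 + 0.08) = 0.40 and a half-width of 2.262 × 0.40/3.162 = 0.29. The increase in variance runs from 1% to 100%.

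**3. Power, if the differences are independent noise.** Assume a two-sided paired t-test at 5% with n = 10, and let s0 be the SD of the change without run error (s0 = √2·s_w). The change detectable with 80% power is 1.00 × s0. With run error, SD(change) = √(s0² + 2·ln(1 + CV²)).

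| s0 (equivalent s_w) | CV 5% | CV 10% | CV 15% | CV 20% |
|---|---|---|---|---|
| 0.3 (0.21) | 78% | 72% | 63% | 54% |
| 0.5 (0.35) | 79% | 77% | 73% | 69% |

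**4. False positives, if every patient has the same shift.** Use the same test with no true change and a bias of ln(1 + shift). Nominal rate 5%.

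| s0 | Shift 5% | 10% | 15% | 20% |
|---|---|---|---|---|
| 0.3 | 7% | 15% | 26% | 40% |
| 0.5 | 6% | 8% | 12% | 18% |

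**5. Which case is nearer.** Study Timelines expects enrolment to take about a year. If entry is even, a single step change in the assay during that year falls between baseline and final for about 20 × 32/365 = 1.8 of the 20 patients. One step therefore cannot shift everyone. A slow drift in one direction could, and step 4 is the limiting case.

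**The case against.** The sentence appears under banking, next to the biorepository text, and can be read simply as saying that samples serve this study and not later research. Holding serum until a patient's last visit would not breach a ban on storage for future use. Blood and tissue are collected under a biorepository protocol that is not among the documents and may set out handling. Objective 2 is exploratory, with 10 patients per cohort, and sampling error dominates: an observed correlation of 0.5 with n = 10 has a 95% Fisher interval of about -0.19 to 0.86 before any assay error. All the magnitudes above are assumed.

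Much of this stands. A reader might infer that nothing is stored at all, that stains as well as serum are certainly run weeks apart, and that drift is certainly added to the change. The documents support none of these. The storage ban is limited to future use, and the biorepository text points to retained material. The grouping of sections for staining is not described. No assay precision is given from which to assert drift.

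What the objection does not remove is the second part of the sentence. Immediate use for serological markers is a statement about timing, and the qualifier on future use does not reach it. A laboratory following it would assay baseline serum before the final serum exists, and nothing in the protocol says otherwise.

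**Conclusion.** The point holds for serum as the text is written, and possibly for stains. Run-to-run variation may be mixed into the Objective 2 before-after change, with no control arm or described run control to separate it.

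The size is unknown. Under the assumed SDs (s_w 0.20 to 0.50, s_run 0.05 to 0.20, log scale, independent runs) the variance of a paired change rises by about 1% to 100%, that is, from negligible to serious. With staggered enrolment most of this would be noise; it becomes bias only to the extent that shifts share a direction across patients. The 4.6-week gap rests on the assumed visit pattern, but the conclusion that the runs differ needs only immediate use and a final sample weeks after baseline.

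Low to medium priority: an inexpensive improvement to an exploratory objective, not a flaw that invalidates it.

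**What to change.** Amend Data and Specimen Banking as follows:

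- Hold serum aliquots (frozen) and fixed tissue blocks within the study until the patient's last sample is in, once the laboratory confirms that the chosen markers tolerate this.
- Assay all of that patient's serum in one run and stain all of that patient's sections in one run, in an order coded to hide the visit. Collection dates should not be visible to the reader.
- Keep flow cytometry fresh, with a common reference control in each run, and report the between-run CV.
- State that this is within-study holding and not storage for future use, and reconcile it with the biorepository text in Procedures Involved, Data and Specimen Banking and the inclusion criteria.

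The cost is short-term freezer space, later laboratory results and possibly a change to the consent wording. No extra visits or samples are needed. Sharing Results with Participants says biopsy and serology results are not given to patients, so the wait delays nothing they would receive.
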